7.3 Data Derivations

Preoperative values will be considered as all assessments prior to surgery.

Baseline values will be considered as the last non-missing assessment prior to first dose of study drug.

Treatment-emergent events will be considered as any event occurring after the initiation of study drug.

The following calculations from Appendix F of the study protocol will be used for the echocardiographic assessments:

- EOA (aortic position) = CSA*VTI₁/VTI₂
- Mitral orifice area: MOA = CSA*VTI₁/DVI
- MOA by pressure half-time method: MOA1/2 = 220/PHT
- Peak pressure drop (aortic valve): Peak $\Delta P_a = 4(v_1^2 v_2^2)$
- Mean pressured difference (a ortic valve): Mean $\Delta P = p_1 p_2$
- Peak pressure drop (mitral valve) Peak $\Delta P_m = 4v_m^2$
- Cardiac output: CO = CSA*VTI₁*BPM
- Indexed EOA: EOAI = EOA/BSA
- Cardiac index: CI = CO/BSA
- Performance Index: PI = EOA/GOA
- Body surface area: BSA $(m^2) = [Weight(kg)^{0.425} * Height(cm)^{0.725}] * 0.007184$

8. STUDY POPULATION

8.1 Demographic Characteristics

Demographic data will be summarized with descriptive statistics, by treatment group, for age and gender. Treatment group differences will be assessed with a two-sample Z-test for age and a chi-square test for gender.

8.2 Inclusion/Exclusion Criteria

Inclusion/Exclusion criteria outcomes will be included in a data listing showing whether subjects met all criteria.

8.3 Randomization Deviations

All deviations regarding the randomization of subjects to study drug will be included in a data listing.

8.4 Prior and Concomitant Cardiovascular Procedures

Concomitant cardiovascular procedures will be summarized by type (e.g. CAB, valve repair, ASD, VSD, etc.) and the valve repaired. Treatment group differences will be assessed with a Chi-square test. The data listing will also include the prior cardiovascular procedures.

8.5 Preoperative Characteristics

Predominant cardiac rhythm, disease etiology, valvular lesions, pre-operative anticoagulation, preoperative risk characteristics, and blood tests will be summarized with descriptive statistics by treatment group. Quantitative characteristics will be assessed for treatment group differences with a two-sample Z test and qualitative characteristics will use the Chi-square test of association between treatment groups.

All Preoperative characteristics will be included in data listings. Data included will consist of cardiac rhythm, disease etiology, valvular lesions and location, anticoagulation use, risk characteristics, blood test, and risk group.

8.6 Operation Data

Aortic and Mitral valve size and cross clamp time will be summarized with descriptive statistics by treatment group. Treatment group differences will be assessed with a two-sample Z test for cross clamp time and with the chi-square test for valve size.

All operative data will be included in data listings to include the following: complete valve information, suture technique, cross clamp time, cardioplegia, and Intraoperative drugs.

8.7 Intraoperative Adverse Events

Intraoperative AEs will be summarized with descriptive statistics by treatment group. The chi-square test will be used to assess the association between treatment groups. A data listing will also be included.

9. SAFETY ANALYSIS

9.1 Primary Analysis

The primary study endpoints are the binary measure of occurrence or not of valve thrombosis, thromboembolism, all major and minor bleeding events whether or not related to valve, reoperation, explant and death. Additionally, the sum of all TEs (including valve thrombosis events) and major bleeding will be included with the primary endpoint analyses.

For each of these binary endpoints, a Kaplan-Meier (KM) life table will be fitted and used to compare each valve treatment group and its control group. The KM analysis will adjust for select risk factors

including age and gender. In addition, the linearized rates as well as overall percentages of occurrences will be included in summary tables. Comparisons of overall percentages between each valve treatment group and its control will be made using a chi-square test or Fisher's exact test as appropriate. Linearized rates will be analyzed for differences between treatment and control groups with relative risks and 95% confidence intervals.

Analyses of mitral valve subjects will also be stratified by location (North America versus Italy) in the summary tables.

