Test Group III, (regardless of risk) – First 3-months postoperation, Coumadin at an INR target of 2.5 to 3.5 with 81 mg/day (75 mg/day in Italy) aspirin will be used. After 3-months, Coumadin dose will be reduced to an INR target of 2.0 to 2.5 with 81 mg/day (75 mg/day in Italy) of aspirin continued.

Control Group – Postoperatively Coumadin with an INR target on 2.5 to 3.5 with 81 mg/day (75 mg/day in Italy) aspirin throughout the study.

D. Sample Size

A sample size estimate was conducted based on FDA OPC criteria^[1]. The study is expected to test the safety of low dose (LD) therapy for anticoagulant therapy in On-X valve patients with LD therapy consisting of the use of Coumadin in combination with aspirin or the use of antiplatelet therapy alone. This study is designed as a non-inferiority study requiring only that LD therapy is not inferior to standard

Coumadin/aspirin treatment. Testing the superiority of LD therapy with adverse event rates as low as expected would require exposure of a prohibitively large patient group. It was necessary for the sample size calculation to assume an acceptable event rate for the primary endpoints of thromboembolism, thrombosis and bleeding events derived by summing the FDA OPC's. The incident rate of the sum of these three events needs to be at least as low as the OPC sum, 7.3%. Table 1 gives the resulting sample size requirements based on a variety of outcomes.

The number of patients to be enrolled in the clinical trial is based first on the ability to show that linearized adverse event rates for the primary endpoints in the test groups are not inferior to the corresponding control groups and second on the ability to show that all valve related adverse event rates in the test groups do not equal or exceed 2 times the rates determined to be acceptable for mechanical valves.

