For the first criterion above, the test group will need to have less than 6%/ptyr cumulative rate of the three events for the study to reach significance with a randomized patient population of between 150 and 250 per group followed for between 5 and 6.7 years at a statistical power of 80% with type I error of 0.05 and a maximum allowable difference between groups of 1.5%. It is expected that each of 50 centers will be able to enroll an average of 30 patients into the study balanced to provide adequate population in each sub-group, providing sufficient patient-years to test the hypothesis, which under the above conditions is around 1000 as shown in Table 1. Thus the study has 200 patients per group in AVR high risk with an average of 5 years of follow-up, or alternatively 150 patients in AVR low risk averaging 6.7 years of follow-up and and up to 250 MVR averaging 4 years of follow-up, providing the approximately 1000 patient-years per group estimated to meet hypothesis.

For the second criterion above, the established rates are the objective performance criteria (OPC) given in the FDA guidance document ⁽¹⁾. The adverse event rates for which OPCs are established include the primary endpoints of thrombosis, thromboembolism and bleeding and the secondary endpoints of paravalvular leak and endocarditis as listed below:

% per valve year (R_A)
0.8
3.0
3.5
1.5
1.2
1.2

In the comparison to OPCs for each adverse event, the null hypothesis being tested is that the true adverse event rate for each test group is equal to or greater than twice the acceptable rate. Rejecting the null hypothesis would conclude that the rate for the test groups is less than two times the acceptable rate. The null and alternative hypotheses can be written as:

Null hypothesis:	$R \ge 2R_A$
Alternative hypothesis:	$R < 2R_A$

Table 1

Sample Size Estimation for On-X Trial LD Therapy vs. Control

The sample size estimation is based on one-sided proportion test, which tests that the incidence rate of thrombosis, thromboembolism and hemorrhage in the LD therapy groups are at least as low as the control groups.

				Maximum Allowable	
Type I Error	Statistical	Expected	Expected	Difference	Needed
(One-sided	Power	Proportion	Proportion	between Two Groups	Patient
Test)		In Control	In Low Dose	to Declare Non-inferiority	Years
		Group	Group		
0.05	80%	7.3%	4.5%	2.0%	309
			5.0%	2.0%	398
			6.0%	2.0%	719
			7.3%	2.0%	2112
			4.5%	1.5%	381
			5.0%	1.5%	504
			6.0%	1.5%	992
			7.3%	1.5%	3739

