The primary study endpoints are the rates of occurrence of valve thrombosis, thromboembolism, all major and minor bleeding events whether or not related to drug therapy, reoperation, explant and death. Other valve related adverse events including endocarditis, hemolysis, hemolytic anemia, paravalvular leak and structural and non-structural dysfunction are secondary endpoints. All events shall be as defined by the AATS/STS guidelines ^[2] for reporting valve study results.

Effectiveness -

Effectiveness endpoints are also secondary endpoints and shall be New York Heart Association (NYHA) functional classification and the echocardiographic hemodynamic parameters of peak and mean gradient and effective orifice area (EOA). Echocardiographic exams shall also evaluate indexed EOA, performance index, cardiac output, cardiac index and amount and location of any valvular regurgitation.

B. Follow-up Regime and Intervals

The intent of the study design is to treat mechanical valve patients with less aggressive anticoagulation. The control group drug regimes are those from the recommendations for mechanical valves of the ACCP^[3] and the AHA/ACC^[4], while test group regimes are either a clopidogrel/aspirin mix for low risk aortic patients or reduced Coumadin to just below the present recommendations but with aspirin added. Patients will be maintained on Coumadin/aspirin beginning immediately postoperatively, with heparin used from operation until INR target is reached. Randomization and transfer to test group will occur at the 3-month visit. INR control will be accomplished using home monitoring with the system provided by QAS or in Italy with systems as provided within the processes used in medical care there. The patient in consultation with his/her physician will also make drug dosage adjustments.

Patients will be followed at 3 months, 6 months and 1-year, then annually thereafter until the study is completed when the patient groups reach sufficient patient-years experience at up to 8-years of follow-up for any individual patient and at least 1-year follow-up for all patients. Visits will be scheduled within 1-month of the appropriate anniversary. Follow-up will be conducted by physician visit.

C. Investigational Procedures

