9.2 Secondary Analysis

Secondary safety study endpoints are the occurrence or not of other valve related adverse events including endocarditis, hemolysis, hemolytic anemia, paravalvular leak and structural and non-structural dysfunction. All events shall be as defined by the AATS/STS guidelines [Akins CW, Miller DC, Turino MI, et al] for reporting valve study results.

For each of these binary endpoints, a Kaplan-Meier life table will be fitted and used to compare each valve treatment group and its control group. The KM analysis will adjust for risk factors age and gender. In addition, the linearized rates as well as overall percentages of occurrences will be included in summary tables. Comparisons of overall frequencies and percentages between each valve treatment group and its control will be made using a chi-square test or Fisher's exact test as appropriate. Linearized rates will be analyzed for differences between treatment and control groups with relative risks and 95% confidence intervals.

Analyses of mitral valve subjects will also be stratified by location (North America and Italy) in the summary tables.

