9.3 Complications and Death

All Complications will be included in comprehensive data listings sorted by treatment group and subject. Any AEs resulting in death will be included in a separate data listing.

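### Kaplan-Meier life tables for the non-fatal endpoints make no provision for death as a competing event, so the absolute cumulative risks will be modestly overstated

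*SAP*

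**What the plan says.** SAP 9.1 lists the primary endpoints (valve thrombosis, thromboembolism, major and minor bleeding, and "reoperation, explant and death") and adds the sum of thromboembolism, including valve thrombosis, and major bleeding. SAP 2.3.1 makes that sum the primary decision criterion. For each endpoint "a Kaplan-Meier (KM) life table will be fitted and used to compare each valve treatment group and its control group". SAP 9.2 applies the same method to endocarditis, hemolysis, leak and the other valve events: "a Kaplan-Meier life table will be fitted and used to compare each valve treatment group and its control group". Protocol III.H also names Kaplan-Meier life tables, together with linearized rates. The display list in SAP 14.1 contains many life-table figures by risk group, so the curves are planned outputs.

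Death is an endpoint in its own right. For deaths linked to adverse events, SAP 9.3 adds a listing: "Any AEs resulting in death will be included in a separate data listing". Neither document says how a death is handled when another endpoint is analysed, and neither plans a cumulative incidence estimate. Protocol III.B allows follow-up "at up to 8-years of follow-up for any individual patient".

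SAP 9.1 and 9.2 also report linearized rates, with relative risks and 95% confidence intervals, and crude percentages of patients with each event.

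**The concern.** A patient who has died can no longer have a thrombosis, a bleed or an explant. If deaths are censored, Kaplan-Meier treats those patients as if they stayed at risk like the survivors. One minus Kaplan-Meier then describes a population in which nobody dies, and it exceeds the proportion actually affected whenever deaths occur.

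The trial asks whether patients can safely be kept on less anticoagulation. Readers will take the curves as the risk that patients actually face. If mortality differs between arms, the vertical gap between the curves also stops being the difference in actual risk.

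**Working it through.** **Plan's own figures.** The documents state no death rate, no cumulative risk and no figure for this bias. The nearest design figure is Table 1 of Protocol II.D: 992 patient-years per group for 7.3% against 6.0%, margin 1.5%, one-sided 0.05, 80% power. With unpooled variance, (1.645 + 0.842)² × (0.073 × 0.927 + 0.060 × 0.940) / (0.015 + 0.013)² = 979, within 1.3% of 992. The concern does not dispute that figure.

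**Inputs.**
- Event rates: the objective performance criteria (OPC) in Protocol II.D, 0.8, 3.0, 3.5, 1.5, 1.2 and 1.2% per valve-year. The row labels are not legible in the available text. I read them as thrombosis, thromboembolism, all bleeding, major bleeding, leak and endocarditis (assumption). The first three add to 0.8 + 3.0 + 3.5 = 7.3, which agrees with the stated sum: "The incident rate of the sum of these three events needs to be at least as low as the OPC sum, 7.3"%.
- Decision composite: 3.0 + 1.5 = 4.5%/yr if thrombosis is already inside the thromboembolism rate, or 0.8 + 3.0 + 1.5 = 5.3%/yr if it is added.
- Reoperation and explant: no rate given; assumed 0.5-2%/yr.
- Death: no rate given; assumed 1-3%/yr. The 5% annual attrition in Protocol II.D is not a death rate.
- Horizon: 8 years (individual maximum) and 5 years. Protocol II.D plans averages of 4 to 6.7 years.

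**Formulas**, with constant event hazard h, death hazard d and time t:
- One minus Kaplan-Meier, deaths censored: 1 − exp(−ht).
- Cumulative incidence, death competing: h/(h + d) × [1 − exp(−(h + d)t)].

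Example, thromboembolism at 8 years with 2%/yr deaths: 1 − exp(−0.24) = 21.34%, against 0.03/0.05 × [1 − exp(−0.40)] = 19.78%. The overstatement is 1.56 points.

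| Endpoint | Rate, %/yr | 1 − KM at 8 y, % | Overstatement at 8 y, deaths 1 / 2 / 3%/yr (points) | At 5 y, deaths 1-3%/yr (points) |
|---|---|---|---|---|
| Thrombosis | 0.8 | 6.2 | 0.24 / 0.47 / 0.68 | 0.10-0.28 |
| Thromboembolism | 3.0 | 21.3 | 0.80 / 1.56 / 2.28 | 0.33-0.97 |
| All bleeding | 3.5 | 24.4 | 0.91 / 1.77 / 2.59 | 0.38-1.11 |
| Major bleeding | 1.5 | 11.3 | 0.43 / 0.84 / 1.23 | 0.18-0.51 |
| Leak, or endocarditis | 1.2 | 9.2 | 0.35 / 0.68 / 1.00 | 0.14-0.41 |
| Reoperation or explant (assumed, low) | 0.5 | 3.9 | 0.15 / 0.30 / 0.43 | 0.06-0.18 |
| Reoperation or explant (assumed, high) | 2.0 | 14.8 | 0.56 / 1.09 / 1.60 | 0.23-0.67 |
| Decision composite (low) | 4.5 | 30.2 | 1.11 / 2.16 / 3.16 | 0.48-1.39 |
| Decision composite (high) | 5.3 | 34.6 | 1.25 / 2.44 / 3.57 | 0.55-1.59 |

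**Death rate needed for a 2-point overstatement at 8 years:** about 1.6-1.8%/yr for the composite, 2.3 for all bleeding, 2.6 for thromboembolism, 5.1 for major bleeding and 10.6 for thrombosis.

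**Between arms.** With 7.3 against 6.0%/yr events and 2%/yr deaths in both arms, the 8-year difference is 6.1 points by one minus Kaplan-Meier and 5.7 by cumulative incidence. With 6%/yr events in both arms but deaths of 2 against 3%/yr, both Kaplan-Meier curves stand at 38.1%, while the actual risks are 35.5% and 34.2%. The first comparison correctly shows equal event hazards; it does not show the difference in actual risk.

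**The case against.** The strongest reply is that little depends on these curves. Protocol II.D frames its first criterion as non-inferiority of linearized rates and its second as a comparison of rates with the OPCs. Events per patient-year are not inflated when exposure ends at death. Using Kaplan-Meier to compare arms remains a valid comparison of cause-specific hazards. SAP 9.1 also gives crude percentages, which project no events onto the dead. All of this stands, and it limits the point to the absolute curves and the absolute gap between them.

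The size also rests on assumptions. Terminal illness and emergency status are exclusions, randomization comes at about 3 months, and a fatal embolism or bleed counts as an endpoint event, not a competing death. On the other side, the high-risk aortic group includes ejection fraction below 30%, chronic atrial fibrillation and vascular pathology, so deaths cannot be assumed negligible. OPC rates may include repeat events whereas Kaplan-Meier counts first events, so the table may run high. Eight years is the individual maximum, and the SAP names no 8-year estimate. Sampling error is of similar size: for a risk of 21% in 200 fully followed patients, √(0.21 × 0.79/200) = 2.9 points. But this bias has a known direction and does not shrink with more patients.

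A reader might infer that the SAP orders deaths to be censored. It does not. Censoring is the default meaning of a Kaplan-Meier analysis of a non-fatal endpoint, and the documented gap is that no rule is given.

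**Conclusion.** The point holds as a modest improvement in reporting. As planned, one minus Kaplan-Meier will overstate absolute cumulative risk for every endpoint other than death. Under constant hazards, OPC event rates and an assumed 1-3%/yr deaths, the 8-year overstatement runs from about 0.2 to 2.6 points for thrombosis, thromboembolism and bleeding, 0.15 to 1.6 for reoperation or explant, and 1.1 to 3.6 for the decision composite. At 5 years it is less than half of this.

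Two stronger readings are tempting. One is that all these endpoints are overstated by 2 to 4 points. The documents give no death rate to support that, and within the assumed range only the composite covers most of that span: thromboembolism and all bleeding pass 2 points only near the top of the range, and thrombosis, reoperation and explant never do. A figure close to 4 points (3.9) arises with 6%/yr events and 3%/yr deaths, but 6%/yr is the design sum that includes all bleeding, not the SAP composite with major bleeding only. The other is that the test-versus-control conclusion is biased. It is not: linearized rates, relative risks and cause-specific comparisons are unaffected.

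**What to change.** In SAP 9.1 and 9.2:
- Report Aalen-Johansen cumulative incidence, by arm, for every endpoint other than death and for the decision composite. The competing event is any death that is not itself the endpoint event.
- State that deaths are censored only for the cause-specific comparison between arms, and keep that comparison for the treatment effect.
- Keep Kaplan-Meier for death, and as a supplementary display for the other endpoints.
- Update the life-table figures in SAP 14.1 to match.

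The cost is SAP wording and one further estimate per endpoint. Event and death dates are already collected on CRF 4. The small downside is a second set of curves, which need clear labels.

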4. SAMPLE SIZE CONSIDERATIONS

The study is expected to test the safety of low dose (LD) therapy for anticoagulant therapy in On-X valve patients with LD therapy consisting of the use of Coumadin® in combination with aspirin or the use of antiplatelet therapy alone. The sample size for this study was designed as a non-inferiority study requiring only that LD therapy is not inferior to standard Coumadin®/aspirin treatment. It was necessary for the sample size calculation to assume an acceptable event rate for the primary endpoints of thromboembolism, thrombosis and bleeding events derived by summing the FDA OPC's. The incident rate of the sum of these three events needs to be at least as low as the OPC sum, 7.3%.

The test group will need to have less than 6%/ptyr cumulative rate of the three events for the study to reach significance with a patient population of 200 per group followed for 5 years at a statistical power of 80% with type I error of 0.05 and a maximum allowable difference between groups of 1.5%.

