6.2 Strata and Covariates

All primary and secondary analyses utilizing Kaplan-Meier life tables will be stratified by risk factors including age and gender. Additionally, MVR treatment groups will be stratified by continent (e.g. North America vs. Italy) for all primary and secondary endpoints.

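### The adjusted Kaplan-Meier comparison in SAP 9.1 and 9.2 has no defined method, and the only hypothesis tests named use crude percentages that ignore follow-up time

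*SAP*

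**What the plan says.** SAP 9.1 gives three between-arm comparisons for each primary endpoint.

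- **Kaplan-Meier.** "a Kaplan-Meier (KM) life table will be fitted and used to compare each valve treatment group and its control group". On covariates: "The KM analysis will adjust for select risk factors", with age and gender as the examples. No log-rank test, regression model or fixed-time contrast is named.
- **Overall percentages.** These comparisons "will be made using a chi-square test or Fisher's exact test as appropriate".
- **Linearized rates.** "Linearized rates will be analyzed for differences between treatment and control groups with relative risks and 95% confidence intervals". The method for the interval is not given.

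SAP 9.2 repeats the scheme for the secondary safety endpoints. SAP 6.2 describes the covariate handling differently: "All primary and secondary analyses utilizing Kaplan-Meier life tables will be stratified by risk factors including age and gender". It gives no age categories.

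SAP 2.3.1 says which endpoint decides (the sum of thromboembolic events, including valve thrombosis, and major bleeds). No section says which of the three analyses of that endpoint decides.

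Protocol II.D sets the first criterion as non-inferiority of linearized rates. Protocol III.H plans Kaplan-Meier life tables and linearized rates, and mentions plain percentage comparisons only for data up to 3 months after surgery. Protocol III.B allows "up to 8-years of follow-up for any individual patient and at least 1-year follow-up for all patients".

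**The concern.** There are two separate weaknesses.

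First, the adjusted analysis is not defined. *Adjust* in 9.1 and *stratified* in 6.2 are different operations, the word *select* leaves the 9.1 covariate list open, and age has no cut-points. Two analysts following this text could report different adjusted results, and the choice would be made after the data are in hand.

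Second, the percentage test counts a patient seen for 1 year the same as one seen for 8. Among randomised arms this does no harm while follow-up is alike. If the low-dose arm were followed for less time, it would show fewer events for that reason alone. In a trial meant to show that reduced anticoagulation is safe, that error runs in the reassuring direction. A crude percentage is also on a different scale from the margin, which was set with rates per patient-year.

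**Working it through.** **Inputs from the documents.** Control rate 7.3%, test rate 6.0%, margin 1.5%, one-sided 0.05, power 80%, 992 patient-years per group (Protocol II.D, Table 1). SAP 4 plans "a patient population of 200 per group followed for 5 years at a statistical power of 80" per cent. Individual follow-up is 1 to 8 years (Protocol III.B).

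**Assumptions.** Constant hazards, and arm-specific withdrawal. The documents give only one attrition figure, 5% a year, for the comparison with objective performance criteria and not by arm.

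**1. The plan's own figure.** Treat patient-years as units in a one-sided non-inferiority test of two proportions. The distance to the margin is 0.015 − (0.060 − 0.073) = 0.028. The unpooled variance is 0.060 × 0.940 + 0.073 × 0.927 = 0.1241.

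- Unpooled: (1.645 + 0.842)² × 0.1241 / 0.028² ≈ 979.
- Farrington-Manning restricted variance: 991.2, which rounds up to 992. This formula reproduces all 24 rows of Table 1.

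The sample size therefore rests on a difference in rate per patient-year, not on the percentage of patients with an event.

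**2. Crude percentages against the margin.** The percentage with an event by time T is 1 − exp(−rate × T).

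| T (years) | 7.3%/yr | 8.8%/yr (control + margin) | Difference (points) |
|---|---|---|---|
| 1 | 7.0 | 8.4 | 1.4 |
| 5 | 30.6 | 35.6 | 5.0 |
| 8 | 44.2 | 50.5 | 6.3 |

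The same 1.5%/yr excess takes a different value at each length of follow-up, so a percentage difference cannot be read against the margin.

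**3. Unequal withdrawal, equal true rates.** With event hazard h = 0.073, withdrawal hazard w and a cap at T years, the crude percentage is h/(h + w) × [1 − exp(−T(h + w))].

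| T (years) | Control, w = 0.05 | Low dose, w = 0.08 | Low dose, w = 0.10 | False advantage (points) |
|---|---|---|---|---|
| 5 | 27.3 | 25.5 | 24.4 | 1.8 to 2.8 |
| 8 | 37.2 | 33.7 | 31.6 | 3.5 to 5.5 |

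Differences are taken before rounding. Subtracting the rounded 8-year figures gives 5.6 at the upper end.

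**4. Error rates by simulation.** 200 per arm, exponential time to first event, uniform individual follow-up, four strata with hazards 0.7 to 1.3 times the arm rate, 4000 runs, two-sided 0.05. Control is followed 1 to 8 years throughout. Entries are the percentage of runs rejecting.

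| Test rate; test-arm follow-up | Chi-square | Stratified log-rank | Rate ratio |
|---|---|---|---|
| 7.3%/yr; 1–8 y | 4.8 | 5.1 | 5.0 |
| 7.3%/yr; 1–6.5 y | 14.6 | 5.3 | 5.5 |
| 8.8%/yr; 1–6.5 y | 4.7 | 15.9 | 16.3 |

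With equal follow-up the chi-square is valid. With shorter test-arm follow-up it rejects too often when the rates are equal, and in the last row its chance of detecting a real excess falls to the null level. The time-based methods keep their error.

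**5. Power cost with equal follow-up.** At 7.3 against 4.5%/yr, with uniform 1 to 8 years in both arms, simulated power to show a difference is 0.61 for chi-square and 0.63 for log-rank: about 2 points.

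**The case against.** **The analysis can be run.** A reader might infer from 9.1 that the primary time-to-event analysis cannot be carried out. The documents do not support that. SAP 6.2 provides for stratification; stratified curves can be drawn, and a stratified log-rank test gives one covariate-adjusted comparison. The gap is in specification: no test, no age categories, and two words for one step.

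**Follow-up time is not ignored everywhere.** A reader might also infer that a chi-square is the only between-arm comparison. Fisher's exact test is named too, and the relative risk of linearized rates with its interval is a planned inference on patient-years. This stands in full. What remains is that the rate comparison is not designated decisive and is not tied to the 1.5% margin.

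**The percentage test has no stated decision role.** It tests for a difference, not non-inferiority, and Protocol II.D puts the criterion on linearized rates. So the documents do not show that a biased percentage would produce a non-inferiority claim. They also do not prevent it from being read as supportive evidence, because 9.1 ranks none of its three comparisons.

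**Unequal follow-up is assumed.** Protocol III.F has removal rules for test patients after an event, but also keeps those patients in follow-up and in their group under intent-to-treat. Differential withdrawal is a risk, not a documented fact. The 8-year figures describe the individual maximum; the SAP's own 5 years gives roughly half as much.

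**Conclusion.** The concern holds as a defect of specification and of method choice. The adjustment claimed for the Kaplan-Meier analysis is not something that estimate can provide. The stratification that could stand in for it is incomplete, and the named hypothesis tests discard follow-up time that the trial collects.

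Its size depends on follow-up by arm. If that is equal, the error rate is unaffected and the power loss is about 2 points. Under the assumed withdrawal of 5%/yr against 8 to 10%/yr, with constant and equal 7.3%/yr event rates, the false low-dose advantage is about 1.8 to 2.8 points at 5 years and 3.5 to 5.5 at 8 years. The documents neither establish nor exclude such a difference in withdrawal. The change should be made because a better comparison is already half-planned and needs no new data.

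**What to change.** In SAP 9.1 and 9.2:

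1. Present overall percentages descriptively and drop the chi-square and Fisher tests as inferential comparisons of these endpoints.
2. Make the patient-year rate comparison the lead analysis. For the decision endpoint in 2.3.1, report the rate difference with a confidence bound set against the 1.5% per patient-year margin, and state the interval method. Fix the confidence level too: the sample size uses one-sided 0.05, while SAP 6.5 sets two-sided 0.05.
3. Replace the statement that Kaplan-Meier will adjust with one named supporting analysis, timed from randomisation: either a log-rank test stratified by gender and stated age categories, or a Cox model with treatment, age and gender. For the mitral groups, stratify by continent as SAP 6.2 already intends.
4. Keep unadjusted Kaplan-Meier curves for display.
5. Align SAP 6.2 with the chosen method, and close the covariate list.

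The cost is SAP wording and standard SAS procedures. A Cox model adds a proportional-hazards check. Its hazard ratio has no margin in these documents, so it should support the non-inferiority decision, not make it.
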